## **2 STUDY OBJECTIVES**

### **2.1 PRIMARY OBJECTIVE**

To demonstrate the effects of dopaminergic activation on the autonomic nervous system in subjects with. The primary endpoint is the effect of bromocriptine-QR on changes in autonomic function measured by assessing sympathetic and parasympathetic function using conventional measures of autonomic function, including power spectral analysis of heart rate as well as peripheral autonomic function using sudorimetry and laser scanning of peripheral microvascular autonomic control.

### **2.2 SECONDARY OBJECTIVES**

To demonstrate the effects of dopaminergic activation with bromocriptine-QR on the regulation of plasma neuroendocrine factors such as the hypothalamic-pituitary-axis (HPA) hormones, and on the plasma levels of markers of inflammation and oxidative/nitrosative stress in type 2 diabetes subjects. The study will evaluate treatment effects on inflammatory markers, the leptin/adiponectin system, and hormonal levels of renin-angiotensin system (RAS), aldosterone and cortisol. Specifically, we will evaluate the following markers of inflammation and oxidative/nitrosative stress: 1) CRP, 2) IL6, 3) TNF  $\alpha$ , 4) PAI1, SOD, TBARS and ADMA and nitrotyrosine as well as other markers of oxidative/nitrosative stress. The study will evaluate the leptin/adiponectin system by measuring total adiponectin (TA), high molecular weight (HMW) adiponectin, leptin, and their ratios (TA/leptin and HMW adiponectin/leptin). A co-secondary objective of the study will be to assess the impact of bromocriptine-QR vs Placebo on measures of insulin resistance and glycemic control (e.g., OGTT glucose and insulin, Matsuda index, HOMA-IR, HbA1c).

The treatment effects on all of the above primary and secondary outcomes will also be assessed as a function of the duration of diabetes and other baseline demographics such as HbA1c, concomitant medications and metabolic status.

## **3 STUDY DESIGN, DURATION AND DATES**

### **3.1 STUDY DESIGN**

This is an interventional, twenty-four week, randomized, double blind, placebo-controlled trial with bromocriptine-QR in subjects with early diabetes and established T2DM to evaluate its effects on the cardiovascular and peripheral autonomic nervous system, as well as on inflammatory markers, the leptin/adiponectin system, hormonal levels of RAS and HPA, indices of insulin resistance and glycemic control, and measures of oxidative and nitrosative stress. A total of 80 subjects are planned to be enrolled in the study. At least 20 and no more than 40 early diabetes subjects and at least 40 but no more than 60 subjects with established diabetes will be enrolled in the study and each randomized to treatment with bromocriptine-QR or placebo. Subjects will be required to be on a stable anti-diabetes regimen consisting of either diet and/or oral anti-diabetic agents consisting of

metformin alone or metformin plus an insulin secretion enhancer (sulfonylurea, DPP4 Inhibitors, or GLP-1 analogs) for at least 60 days prior to randomization. Following a 2 week lead-in period, subjects will be randomized in a 1:1 ratio to receive UDT (usual diabetes therapy) plus bromocriptine-QR or UDT plus placebo. Subjects must have a documented C-peptide level of >2 ng/ml from the screening visit. The circadian timing of the interventional therapy will be within 2 hours of waking in the morning. Following randomization subjects will be titrated to the maximum tolerated dose of the study drug over a four-week period. During these first 4 weeks, the daily dose of the study drug will be titrated up by one tablet (0.8 mg bromocriptine-QR or 1 matching placebo tablet) per day on a weekly basis until a maximal tolerated dose of at least two tablets (1.6 mg/day bromocriptine-QR or 2 placebo tablets) and no more than four tablets (3.2 mg/per day b-QR or 4 placebo tablets) is achieved. During the first 4 weeks of the study, subjects will be called weekly to monitor for possible adverse events. Subjects will be maintained at their maximum tolerated dose of between two to four tablets per day (1.6 to 3.2 mg bromocriptine-QR per day or 2 to 4 placebo tablets) for the duration of the study. Subjects unable to tolerate two tablets per day of study drug will be terminated from the study and any further analyses. Subjects will be seen at 4 weeks after randomization, at 12 weeks after randomization, and then at study end (week 24 or early termination). A primary analysis of the primary and secondary endpoints will be performed after 12 weeks with a secondary analysis conducted on these study endpoints at 24 weeks. Subjects will be contacted 30 days after stopping the study drug to record any adverse events that occurred after cessation. During the study period subjects will be advised to perform home blood glucose monitoring at least on a daily basis. Subjects will be required to continue their usual anti-diabetes regimen during the study but will be allowed to alter the dosages of these medications and/or add or subtract medications as deemed necessary by the Principal Investigator to optimize blood glucose control to avoid hypoglycemia or persistent hyperglycemia. In any case, rescue therapy for hyperglycemia will be administered if a subject has two consecutive fasting glucose measurements >270 mg/dL spaced  $\leq 7$  days apart before week 12, or two consecutive fasting glucose measurements >250 mg/dL spaced  $\leq 7$  days apart or a HbA1c >11% at or after week 12. The choice of rescue therapy will be at the discretion of the Principal Investigator and may include adjustments in the dosages of the medications that the subject is already on and/or addition of other glucose lowering therapies. The subjects with concurrent antidiabetes medication changes may remain "on study" for the remainder of the study until week 24 undergoing all evaluations if in the opinion of the investigator this does not pose any serious risk to the subject or the study objectives unless the rescue therapy requires insulin, in which case the subject will be withdrawn from the study as per the exclusion criteria for the study. Subjects will receive a complete physical and neurological exam and clinical laboratory assessments at baseline and at the completion of the study. The primary and secondary endpoints will be evaluated at baseline, week 4, week 12, and week 24 or at early termination. Subjects will be evaluated using the procedures listed below.

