## Study Design

This is a single-site, prospective, interventional, twenty-four week, randomized, double blind, placebo-controlled trial with bromocriptine QR in subjects with early diabetes and established T2DM to evaluate its effects on the cardiovascular and peripheral autonomic nervous system, as well as inflammatory markers, the leptin/adiponectin system, hormonal levels of RAS and HPA axis, indices of insulin resistance and glycemic control, and measures of oxidative and nitrosative stress. At least twenty (20) but no more than forty (40) early diabetes subjects and at least forty (40) but no more than sixty (60) subjects with established diabetes will be enrolled in the study.

Entry criteria will be checked at the screening visit. Subjects will be required to be on a stable anti-diabetes regimen consisting of diet and/or oral anti-diabetic agents consisting of metformin alone or metformin plus an insulin secretion enhancer (sulfonylurea, DPP4 Inhibitors, or GLP-1 analogs) for at least 60 days prior to randomization. Following a 2 week lead-in period, subjects will be randomized in a 1:1 ratio to receive UDT (usual diabetes therapy) plus bromocriptine-QR or UDT plus placebo. The circadian timing of the interventional therapy will be within 2 hours of waking in the morning.

Following randomization, subjects will be titrated to the maximum tolerated dose of the study drug (bromocriptine-QR or placebo) over a 4 week period.

Subjects will return at 4 weeks after randomization, at 12 weeks after randomization, and then at study end (week 24 or early termination) for analyses of the primary and secondary endpoints. A primary analysis of the study data will be performed after 12 weeks with a secondary analysis conducted at 24 weeks. Subjects will be contacted 30 days after stopping the study drug to record any adverse events that occurred after cessation.

All visits will be conducted at The Strelitz Diabetes Center, Norfolk, VA.

---

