# STUDY SCHEDULE

Data collected and/or action	Screen	Baseline	Treatment Period (24 weeks)									
	Visit 0	Baseline Visit 1 (Visit 0 + <30 days)	Phone call 1 (Visit 2 + 7 days)	Phone call 2 (Call 1 + 7 days)	Phone call 3 ( Call 2 + 7 days)	Visit 2 Week 4	Phone call 4 Week 8	Visit 3 Week 12	Phone call 5 Week 16	Phone call 6 Week 20	Visit 4 Week 24 (or Early Term)	Phone call 7 Visit 4 +30 days
		Random-ization										
Informed Consent	X											
Entry Criteria	X											
Medical History	X					X		X			X	
Physical Exam	X										X	
Neurological Exam	X										X	
ECG	X										X	
Hematology and chemistry	X										X	
Lipids		X						X			X	
HbA1c	X	X						X			X	
Urine Microalbumin		X						X			X	
Inflammatory oxidative/ nitrosative stress and neuroendocrine Markers		X				X		X			X	
OGTT (with glucose and insulin analyses)		X						X			X	
C-peptide	X							X			X	
HOMA-IR (fasting glucose and insulin)						X						
Autonomic Function Tests		X				X		X			X	
Sudorimetry		X				X		X			X	
Skin Blood Flow		X				X		X			X	
Quantitative Sensory Tests		X				X		X			X	
Study Drug instruction (first dose next AM)		X										
Study Drug Titration reminder			X	X	X							
AE/SAE query/ Study Drug assessment			X	X	X	X	X	X	X	X	X	
Final follow up for AE/SAE resolution												X
Concomitant meds			To be assessed throughout the study									
Adverse Events			To be assessed throughout the study									
Serious Adverse Events			To be assessed throughout the study Report serious adverse events to sponsor within 24 hours									
Mandatory Contact			Weekly titration phone contacts as described in the protocol									

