## 4 SELECTION OF SUBJECTS

### 4.1 NUMBER OF SUBJECTS

A total of up to 80 subjects are planned to be enrolled; At least twenty and no greater than forty early diabetes subjects (diabetes duration of < 4 years) and at least 40 but no greater than 60 subjects with established diabetes (diabetes duration of ≥4 years) will be enrolled in the study.

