### **7.2.2.4 Call 3 (Call 2 + 7 days)**

- Study site will contact the subject by telephone to remind them to increase the dose of bromocriptine-QR to 4 tablets and assess tolerance. Subjects will be instructed to contact the study site if they experience intolerable nausea or vomiting.
- If at any time a subject is not able tolerate the next higher dose of bromocriptine-QR, they may stay at the current dose, providing it is at least 2 tablets per day.
- Assessment for any AE/SAE will be completed
- Subjects will schedule an appointment for the week 4 follow up visit on day 28 ± 3 days

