#### **7.2.2.10 Visit 4 (Visit 1 plus 24 weeks [ $\pm$ 3 days] or Early Termination)**

Subjects will be instructed to arrive having fasted from the night before this visit and having taken their morning dose of the study drug with time taken noted.

- Assessment for any AE/SAE will be completed
- Medical history will be taken
- Routine physical examination will be performed
- ECG test will be performed
- Study drug will be discontinued
- Sudorimetry
  - Sudoscan
- Autonomic Function Tests
  - Heart Rate Variability (HRV)
  -
- Blood will be taken for the determination of HbA1c, lipids, clinical chemistry variables, hematology, c-peptide, inflammatory markers and oxidative/nitrosative stress (see study schedule).
- Total amount of blood drawn at this visit will be approximately 55-60 ml.
- Urine will be obtained for measurement of microalbumin

- An OGTT will be administered and OGTT glucose and insulin levels will be obtained at 0, 30, 60, 90 and 120 minutes post-glucose challenge.
- Skin Blood Flow (SkBF)
  - Continuous Laser Doppler
- Quantitative Sensory Tests (QST)

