## **7.3 STATISTICAL METHODS**

Statistical analyses will be conducted on between group (bromocriptine-QR vs. placebo) differences in change from baseline of all primary and secondary endpoints. The treatment effects on all of the primary and secondary outcomes will also be assessed as a function of the duration of diabetes and other baseline demographics such as HbA1c, concomitant medications and metabolic status. Mean differences of glycemic control, various derivative autonomic function values, and inflammatory marker levels will be compared first using standard Analysis of Variance (ANOVA), with diagnostic group entered as the predictor variable. Within-group analysis for change in primary and secondary endpoints after 12 weeks of treatment will be done using repeated measures MANOVA (multivariate analysis of variance). For glycemic control analysis patients will be stratified according to post-prandial insulin response. If data are not normally distributed, the Wilcoxon signed-rank (within group) or Mann Whitney (between group) tests may be employed or Fisher's exact test in case of small sample sizes. The level of significance will be set at  $p < 0.05$ . Relationships and/or trends between the effect of Cycloset on neurovascular function and diabetic neuropathy will be determined with Spearman's rank correlation.

A statistical analysis plan (SAP), providing details of the analyses and presentation structure of the results, will be developed and finalized before the database is locked.

A local laboratory will be utilized for collection and analysis of the laboratory tests associated with efficacy, and safety. Standardized guidelines for preparation, collection, and centralized analysis of blood specimens will provide uniformity of the data and will avoid potential inter-laboratory variability due to inconsistent methodology.

The analyses of plasma markers of inflammation, oxidative/nitrosative stress, neuroendocrine factors, and the adiponectin/leptin ratio will be conducted at VeroScience (Tiverton, RI).

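### Randomised subjects who cannot tolerate two tablets per day are terminated from the study and from further "analyses" in an ambiguous sense, and no stated efficacy set or missing-data rule keeps them in the comparison

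*Protocol*

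**What the plan says.** Protocol section 3.1 randomises first and titrates over the next four weeks. It then states: "Subjects unable to tolerate two tablets per day of study drug will be terminated from the study and any further analyses". Section 7.2.2.4 (Call 3) is the counterpart for subjects who cannot go higher: "they may stay at the current dose, providing it is at least 2 tablets per day".

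The same section 3.1 says "The primary and secondary endpoints will be evaluated at baseline, week 4, week 12, and week 24 or at early termination". The Study Schedule puts week 24 and early termination in one column, and section 7.2.2.10 treats them as one visit with the endpoint tests listed. Section 9.1 is narrower: withdrawal ends study procedures, and only the safety examinations of the final day are to be done beforehand, as far as possible.

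On who is analysed:

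- Protocol section 7.3: "Statistical analyses will be conducted on between group (bromocriptine-QR vs. placebo) differences in change from baseline of all primary and secondary endpoints". No set is named.
- Protocol section 9.6, headed as analysis populations, gives the 12-week and 24-week time points and says dropouts are replaced. It defines no population.
- Section 9.1 replaces subjects withdrawn within 4 weeks after titration is completed. It does not say clearly whether those who leave during titration are covered.
- SAP, Primary Endpoint: between-group change to week 24, with no set named.
- SAP, Secondary Endpoints 1): glycaemic endpoints in subjects who complete 24 weeks and have both OGTTs. Secondary Endpoints 2) refers to an overall cohort without defining it.
- SAP, Statistical Methods: t-tests on change to week 24, with no missing-data rule. The only instruction on missing data is the case report form rule in Protocol section 12.1.

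**The concern.** Randomisation protects the comparison only if subjects are analysed as randomised. Here a subject can leave the comparison because of how he or she tolerated the assigned tablets, and active drug and placebo need not be tolerated equally. If those who leave would have had different outcomes from those who stay, the retained arms are no longer comparable. Replacement does not repair this: a new subject is kept only if he or she also tolerates the tablets. As the plan stands, there would be no all-randomised result to set beside the retained-subject result.

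**Working it through.** **1. The two readings of the word.** The Protocol Outline uses the same noun for visits held "for analyses of the primary and secondary endpoints", and the Study Schedule and section 3.1 use it for laboratory work, so in "Subjects unable to tolerate two tablets per day of study drug will be terminated from the study and any further analyses" it may mean assessments.

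| Reading | Effect of section 3.1 | Does another passage keep the subject? |
|---|---|---|
| Statistical analyses | Explicit exclusion after randomisation | No |
| Assessments | Testing ends | No set in 9.6 or for the SAP primary endpoint; completers only for glycaemic endpoints; no rule for early-termination values |

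Timing matters. The step to two tablets comes at Visit 1 + 7 days (section 7.2.2.2). The first scheduled endpoint visit after baseline is week 4 ± 3 days (section 7.2.2.5). A subject who fails at two tablets may have only a baseline and one early-termination measurement, and the week-24 t-test has no stated place for the latter.

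**2. The plan's own figure.** Sections 9.6 and 9.7 give no dropout rate. Section 9.7 claims power above 0.80 with 80 subjects (about 40 per arm) at p < 0.05 for a 10% change, without an SD, so the figure can be neither reproduced nor refuted. Taking power as exactly 0.80 with a two-sided t-test (sidedness is not stated), the noncentral t gives a standardised effect d = 0.634, that is, an SD of 10/0.634 = 15.8 percentage points.

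**3. Form of the bias.** Let p be the proportion excluded in an arm and g the mean outcome of retained minus excluded subjects, in SD units. The retained mean differs from the all-randomised mean by p × g, so

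bias = pA × gA − pP × gP (A active, P placebo).

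It is zero if exclusion is unrelated to outcome in both arms (both g = 0), or if rates and gaps are both equal. Equal rates alone are not enough: with 10% in both arms, gA = 0.8 and gP = 0, bias = 0.080 SD and type I error is 0.063 at 36/36.

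**4. Illustration.** All rates and gaps below are assumed, and the gap is the same in both arms, so bias = (pA − pP) × g. Its sign follows the gap. Type I error is two-sided.

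| pA | pP | g | Bias (SD) | Type I error, 40/40 | Retained n | Type I error, retained n |
|---|---|---|---|---|---|---|
| 0.10 | 0.05 | 0.5 | 0.025 | 0.0514 | 36/38 | 0.0513 |
| 0.10 | 0.02 | 0.5 | 0.040 | 0.0536 | 36/39 | 0.0533 |
| 0.10 | 0.05 | 0.8 | 0.040 | 0.0536 | 36/38 | 0.0533 |
| 0.10 | 0.02 | 0.8 | 0.064 | 0.0592 | 36/39 | 0.0586 |
| 0.20 | 0.05 | 0.5 | 0.075 | 0.0627 | 32/38 | 0.0610 |
| 0.20 | 0.02 | 0.5 | 0.090 | 0.0683 | 32/39 | 0.0660 |
| 0.20 | 0.05 | 0.8 | 0.120 | 0.0828 | 32/38 | 0.0783 |
| 0.20 | 0.02 | 0.8 | 0.144 | 0.0975 | 32/39 | 0.0915 |

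Four of the eight combinations stay below 0.06.

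**5. Power cost of keeping everyone.** Assumptions: d = 0.634 in tolerators, no effect in non-tolerators, every subject measured.

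| Case | Existing rule | All randomised |
|---|---|---|
| 10% active, not replaced | 36/38 to 36/39: 0.77 | 40/40, d × 0.9 = 0.571: 0.71 |
| 20% active, not replaced | 32/38 to 32/39: 0.74 to 0.75 | 40/40, d × 0.8 = 0.507: 0.61 |
| 10% active, replaced | 40/40: 0.80 | 44/41 (85), d × 40/44 = 0.577: 0.75 |
| 20% active, replaced | 40/40: 0.80 | 50/42 (92), d × 0.8 = 0.507: 0.67 |

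The replaced cases solve for 40 retained per arm: 40/0.9 ≈ 44 and 40/0.8 = 50 active; 40/0.98 ≈ 41 and 40/0.95 ≈ 42 placebo.

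**The case against.** The best defence has three parts.

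*The sentence may only end testing.* On that reading section 3.1 excludes no one from the statistics, and because early termination shares a visit with week 24, the value taken there could be read as the week-24 value. The SAP does not repeat the exclusion, and its completer restriction covers only the glycaemic endpoints. The ambiguity is real. A reader might infer that the plan certainly drops these subjects from the primary autonomic analysis, and the documents do not establish that. But neither document says that early-termination values count as week 24, and such a rule would not override the completer restriction. On either reading the comparison is undefined for these subjects.

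*The aim is mechanistic.* The objective concerns dopaminergic activation, for which subjects who tolerate the drug are an informative group. That justifies a declared tolerator analysis. It does not replace the all-randomised comparison in a trial whose stated analysis is between randomised groups (Protocol section 7.3).

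*The size is assumed.* This stands in full. A reader might infer that the plan favours bromocriptine-QR, or that its type I error is inflated by a known amount. The documents support neither: with no rate, gap or SD, the bias may have either sign or be nil.

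**Conclusion.** The point holds and should be fixed. Section 3.1 allows, and on one reading requires, the removal of randomised subjects for a reason that can depend on arm. No section or SAP paragraph defines a set or rule that keeps them. Confidence is high that the definition is missing and that the wording needs correcting. Confidence is low on the size of any bias.

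The illustrative bias of 0.025 to 0.144 SD in either direction, and type I error of 0.051 to 0.097, rest entirely on assumed exclusion rates (10–20% active, 2–5% placebo) and gaps (0.5–0.8 SD). The conclusion does not depend on them. The conflict over the primary time point (week 12 in Protocol section 9.6, week 24 in the SAP) is a separate matter to reconcile.

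**What to change.** 1. Strike the final four words of "Subjects unable to tolerate two tablets per day of study drug will be terminated from the study and any further analyses". The rule for stopping study drug is unchanged.
2. In Protocol section 9.6 and the SAP, define the primary efficacy set as all randomised subjects by assigned arm. Replaced subjects stay in, and replacements count as additional randomised subjects. Section 4.1 says "A total of up to 80 subjects are planned to be enrolled"; state whether this counts randomised or retained subjects, since 85 or 92 randomised would exceed it on the first meaning.
3. Reconcile section 9.1 with sections 3.1 and 7.2.2.10, so that the endpoint measures already scheduled for early termination are taken as far as possible.
4. Analyse all post-baseline data in a repeated-measures model by scheduled visit, with the treatment contrast at the declared primary time point. Use an early-termination value only at the visit whose ± 3-day window it falls in; do not relabel it as week 12 or week 24.
5. State that, without off-drug follow-up, later outcomes of subjects who leave in titration are modelled as missing at random, that is, as resembling retained subjects of the same arm with similar observed values. Test this with multiple imputation by arm, including subjects with no post-baseline value, shifting imputed values by −0.8 to +0.8 SD. With 10% or 20% of active values imputed, that moves the estimate by up to 0.10 × 0.8 = 0.08 or 0.20 × 0.8 = 0.16 SD in either direction.
6. Report the tolerator or completer analysis as supportive.

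**Cost.** Text edits and one SAP paragraph, with no new visits. The statistical price is possible dilution, as in step 5 of the working; those powers assume every subject is measured, which this fix does not guarantee. If the last subject finished by August 2018 as planned, the SAP of December 14, 2018 can use only what was measured, and item 3 comes too late.
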